- *What are the health economic impacts of using CFDP?*
 - The study will identify and compare healthcare resource utilisation, and associated costs, of both pathways using data collected from HES, NHS BSA, and local clinical records.

Secondary

- *What are the long-term impacts of treatment in terms of antibiotic use, pain experienced, anxiety, further treatment required by CFDP compared to treatment through a traditional pathway?*
 - Using a text message questionnaire, data will be collected from parents/guardians regarding antibiotic use, pain experienced and anxiety of the patient.
- *What are dental teams' beliefs and views on CFDPs/traditional pathways?*
 - Using a qualitative methodology dental team views will be recorded and analysed.
- *Are patients satisfied with their experience in using CFDPs and traditional services?*
 - Patient experience will be recorded using an adapted version of the NHS Friends and Family Test recorded through a text message questionnaire.
- *Looking only at the CFDPs - what proportion require an onward referral and what characteristics necessitate an onward referral?*
 - The project will assess the characteristics of patients who do and do not require onward referral.
- *Does the scheme work differently across different localities, for different patients?*
 - The project will determine similarities and differences in how CFDP sites operate for the patients they see and treat.

II. INVESTIGATORS

Key Contacts

The Principal Investigator for this study will be:

[name]
University of Manchester
Dental Health Unit
[name]

Other individuals involved in this study include:

[name] [contact]
(University of Manchester; Statistician)

[name] [contact]
(University of Cambridge; Realist evaluation)

[name] [contact]
(University of Manchester)

[name] [contact]
(University of Liverpool; Consultant Dental Public Health)

[name] [contact]
(University of Manchester; Health Economist)

[name]
(Lay co-applicant / PPI advisor)

III. APPROVAL OF THE PROTOCOL

The protocol has been reviewed and approved in writing by NHS ethics (IRAS ID: 323977 REC Reference: 23/EM/0093), and The University of Manchester as sponsor.

The Principal Investigator will ensure all relevant staff participating in the study have appropriate training prior to study commencement.

IV. DURATION OF STUDY

3 Years (see timeline).

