A referring dentist should chart all teeth in a referral indicating all teeth that are carious and which are symptomatic. When deciding triage outcome, if one or two teeth only are symptomatic (i.e., causing pain) and this could be managed by extraction/restoration, then the child would be suitable for management within CFDP. The child should attend the referring dentist for completion of treatment (shared care model).

Not suitable for management in CFDP:

Child who has developmental defects of permanent teeth requiring treatment

Child with three or more symptomatic carious teeth

Child with unrestorable teeth in three or four quadrants e.g., extractions indicated in three or four quadrants

Child who needs root canal treatment (RCT) in permanent teeth

Child with moderate to severe medical complexities

Child with moderate to severe behavioural complexities

VII. STUDY DESIGN Prospective, comparative, observational cohort study

VI: Planned interventions:

The exposed cohort will receive care following triage and treatment through the alternative pathway (treatment through the new CFDP).

The control cohort (non-exposed) will receive care following triage and treatment through the traditional pathway (treatment through the Specialist Paediatric Dental pathway).

Time scale (see appendix for more detailed time line)

Year 1 – 2023

Months Feb-March -Study set up

Months Feb-March -Ethics application

Months March – PPI development,

Months May -December (2024) – Recruitment

Months May - December (2024) – Data collection (CRF)

Months May – September – Observational data collection

Months May – March (2024) -text message survey

Months Nov – Dec – Data coding

Months August to October – Qualitative interviews

Year 2 – 2024

Months Jan -Feb – NHS BSA application

Months May-July – Text message survey

Months May – September – Observational data collection

Months August to October – Qualitative interviews

Months November to December -Qualitative analysis

Year 3 – 2025

Months March – April finalise NHS application

Months May – August -text message survey

Month June – August – NHS data retrieval (NHS BSA, CDS, clinical records, NHS digital, HES)

Month September – November – Data analysis

Month November -Jan – report write up

Year 3 – 2026

Month Jan – March -Dissemination

Outcomes

Proposed outcome measures

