Primary: The primary outcome, measures whether a child has had a dental extraction under General Anaesthetic two years after referral as indicated in electronic patient records (recorded through HES data or through CDS patient records).

Secondary: The secondary outcomes to be considered in this project include:

- Waiting time until first appointment
- Number of sessions of treatment
- Whether a child was successfully seen and treated. For this outcome success is defined as treatment completed by a dentist that results in a child being referred back to their own dentist or discharged, pain free.
- The number of extractions and restorations as reported in NHS BSA data
- The courses of antibiotics taken during wait and treatment
- Participants referred back into the specialist pathway within two years of referral.
- Dental pain experienced by a child
- Participants views of their treatment and engagement with the dental profession (follow up of dental appointment) as indicated by the responses to the text message. Questions will include an adapted version of the NHS Friends and Family Test, questions on satisfaction, possible negative/adverse experiences, possible positive experiences, and an option for free text comments at the end of the survey.

Qualitative work will focus on two groups: (a) dental professionals (incl. triage, in-practice dental teams, CDS teams and referring practices) and (b) patients (incl. parents and children) accessing and using CFDPs.

(a) Dental teams' attitudes and beliefs regarding CFDP will be examined to better understand what worked well, what created barriers and look at how best to support implementation for such initiatives if they become routine practice.

In a qualitative approach, we will explore dental team beliefs, attitudes, and opinions regarding CFDPs and traditional pathways. To allow for the realist evaluation to take place, a combination of focus groups and one-to-one interviews will take place with the triage team and staff at CFDPs.

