A steering group, will monitor this study at periodic intervals. This group will include the Principal Investigator, University of Manchester staff, lay member of the community (Public and Patient Involvement (PPI) to ensure that the study is being conducted according to Good Clinical Practice Guidelines. An Oversight Committee (chaired by [name]) will monitor and feedback to both the research group and NIHR. Further PPI - patient and public involvement - will be sought for various aspects of the study including visits to practices for recruitment opportunities and through organisations which work with parents and children (such as sure start) to gain relevant opinions on the study, for example both the questionnaire and leaflet will be given to parents to fill in to test before the study begins.

The research will be monitored by the Lead Investigator on a weekly basis and at key project milestones.

The study will be subject to the audit and monitoring regime of the University of Manchester.

VIII. Data handling

The data controller will be the University of Manchester. Data will be collected through

- Clinical examinations. Dentists at the CFDP or CDS will fill out a Case report form (CRF) including information on treatment, antibiotic use (see Appendix B) - pseudo anonymised
- Text message surveys. Participants will answer text message survey at baseline, 1 year and 2 years after consent (See Appendix B). Surveys through text message survey (Text messages will be sent to participants using SafeMessage. SafeMessage is operated by FDS Consultants who are an NHS Business Partner (ODS: 8J025) who have met the following regulatory and legislative requirements: Fully completed NHS

DSPT, CyberEssentials Plus, Data stored in HSCN servers within ISO27001 certified, UK only data centres, DCB0219 met, Clinical Safety Officer, Data Protection Officer and Calidcott Guardian. The system is regularly penetration tested and complies with all the requirements of NHS Digital for the safe storage of sensitive data under GDPR.)

Answers from text message survey will be transferred to csv and pseudo anonymised

- Routinely collected data. Following participants consent, data will be linked and collected to be used within the study. This data will come from but not limited to NHS BSA, NHS England, HES, clinical records from the Community Dental Service, GDP and CFDP and referral forms (See appendix B) this data will be pseudo anonymised.

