Indicate if following is requested (GA)	GA no GA
Previous dental history	free text
Main reason for referral	tick box
Teeth requested for treatment within referral	dental chart
Complexity score	tick box
Reason for referral	free text
Medical behaviour indicators	tick box
Patient anxiety question	5 questions on likert scale
radiograph included	yes no
Date of referral	date

Text message survey

	Text message Question	Potential response
1	Does your child have any pain in his/her mouth/teeth at the moment? Please reply: yes or no.	"Yes" / "No"
1a	If yes, how would he/she rate this pain from 1 (not too painful) to 10 (most painful pain ever)?	"1-10"
2	Has your child received any antibiotics for a dental problem recently for example, in the last year?	"Yes" / "No" / "Can't remember"
2a	If yes, do you remember how many days he/she was given and for how long did he/she take them? Just type your answer below.	Open text
3	In the last 3 months, has your child had any of the following problems: pain, difficult sleeping, problems eating/drinking?	"pain" / "sleeping" / "eating/drinking"
4	Overall, how was your experience of the service you attended for your child's dental treatment. Please reply: very good, good, neither good nor poor, poor, very poor?	"very good" / "good" / "neither" / "poor" / "very poor"
5	Did you feel the service your child attended for their dental treatment was appropriate for your child? Please reply: yes definitely, yes to some extent, no	"yes definitely" / "yes" / "no"
6	Would you recommend the service to family and friends? Please reply: yes, no, not sure	"Yes" / "No" / "Not sure"

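### Survey items 4 to 6 do not name the service being rated, so at 1 and 2 years a reply may not refer to the recruiting CFDP or CDS

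*Protocol*

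**What the plan says.** The secondary research questions include "Are patients satisfied with their experience in using CFDPs and traditional services", to be answered by the text message questionnaire. The list of secondary outcomes repeats this as "Participants views of their treatment and engagement with the dental profession (follow up of dental appointment) as indicated by the responses to the text message".

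Appendix B prints the wording. Item 4 reads "Overall, how was your experience of the service you attended for your child's dental treatment", item 5 "Did you feel the service your child attended for their dental treatment was appropriate for your child" and item 6 "Would you recommend the service to family and friends". All three refer to a single, unnamed service. Items 1 to 3 (pain, antibiotics, recent problems) each carry a time reference, and items 4 to 6 carry none. No listed item asks which service the parent has in mind.

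On timing, section VIII (Data handling) states: "Participants will answer text message survey at baseline, 1 year and 2 years after consent". One list of questions is shown, with no version specific to a wave.

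**The concern.** A question about one unnamed service works when a family has used only one. Here a parent answering at 1 or 2 years may have dealt with a CFDP, the family's own dentist, the CDS and a hospital since the referral. The parent cannot tell from the item which of these is meant, and the analyst cannot tell from the reply which was rated.

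At stake is the interpretation of one secondary outcome. The research question is about satisfaction with CFDPs and with traditional services. Replies grouped by recruiting site may be partly ratings of some other service, and then the between-group difference is not clearly a difference between those two services.

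**Working it through.** The plan gives no figure for satisfaction, for onward referral, or for the share of parents who might rate another service. Its sample size (354 per group) concerns general anaesthesia and does not bear on this point. The check is therefore mainly a comparison of sections.

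**Does the Protocol expect more than one service per child?** Yes, in four places.
- The triage text in section V says of children suitable for CFDP management: "The child should attend the referring dentist for completion of treatment (shared care model".
- The definition of successful treatment under Outcomes is treatment that "results in a child being referred back to their own dentist or discharged, pain free". It applies to both groups.
- Onward referral from CFDPs is a secondary research question.
- Referral back into the specialist pathway within two years is a secondary outcome.

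**Can other data show which service was rated?** No. The CDS form in Appendix B has a field for earlier attendance at a CFDP or another service. The forms also record appointments and outcome, and the hospital and CDS extract records the date of any anaesthetic. These data can flag a child who moved, but they do not show what the parent was thinking of.

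**Which waves are exposed?** Mainly those at 1 and 2 years. Consent is normally taken while the family attends the CFDP or CDS, so a baseline reply most naturally refers to that site. Families approached by letter after treatment are an exception.

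**Illustration on assumed values only.** Let the true share answering very good be pC for the CFDP and pT for the traditional service. Let a share a of CFDP families rate another service whose true share is qC, and a share b of traditional families rate one whose true share is qT. Then

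observed difference = [(1 − a)·pC + a·qC] − [(1 − b)·pT + b·qT].

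| Assumed case | Calculation | Observed | True |
|---|---|---|---|
| pC = 0.80, pT = 0.60; 15% of CFDP families rate the specialist service (qC = 0.60) | 0.80·0.85 + 0.60·0.15 − 0.60 = 0.77 − 0.60 | 17 points | 20 points |
| pC = 0.80, pT = 0.60; 15% of traditional families rate a service with qT = 0.80 | 0.80 − (0.60·0.85 + 0.80·0.15) = 0.80 − 0.63 | 17 points | 20 points |
| pC = pT = 0.80; 15% of traditional families rate a service with qT = 0.60 | 0.80 − (0.80·0.85 + 0.60·0.15) = 0.80 − 0.77 | +3 points | 0 |
| pC = pT = 0.80; 15% of CFDP families rate a service with qC = 0.60 | 0.77 − 0.80 | −3 points | 0 |

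The first two rows shrink a real difference. The last two create a false one, in opposite directions. The documents do not say which case applies, or whether 15% is a realistic share.

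**The case against.** The strongest reply is that the study compares pathways. If a CFDP child is later sent on, the family's experience there is arguably a result of having entered the CFDP pathway and not contamination. This stands in part: replies grouped by pathway can be reported as experience of the whole pathway. But the items ask about one service, and the research question names services, so that reading does not answer the question as posed.

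A second reply is that the printed list may not be the whole message. The Outcomes section mentions questions on positive and negative experiences and a free-text field that do not appear in the Appendix B table, and an introductory text could name the site. Section VII also says the questionnaire will be tried out with parents beforehand. This is possible, but nothing shown ties items 4 to 6 to a site.

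A third reply is that analysts can flag children who moved and repeat the analysis without them. This helps to bound the problem. It does not reveal which service was rated, and leaving out children sent on from a CFDP would remove its less successful cases.

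A reader might infer that misattribution is greater in the CFDP group and so biases the difference in a known direction. The documents do not support this. Return to the own dentist is foreseen in both groups, all study children were triaged as suitable for a CFDP, and the CDS form itself anticipates attendance elsewhere. Onward referral is a plausible source specific to CFDPs, but no rate is given. Nor can the 15% planned for general anaesthesia in the sample size stand in for a rate of mis-rating: it would assume that every such family rates the specialist service, and it ignores mis-rating in the traditional group, where 25% is planned.

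**Conclusion.** The point holds as a weakness of wording. At the later waves a reply to items 4 to 6 cannot be tied to the CFDP or the traditional service, so the satisfaction comparison may be blurred. The documents show that parents may rate another service, not that they do. Size and direction are unknown, and every rate in the illustration is assumed.

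It would also go too far to say that nothing can be done afterwards. The baseline wave is less exposed, the choice of wave is an analysis decision, and movement between services can be flagged from records. What cannot be recovered is which service a given parent had in mind.

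The point concerns one secondary outcome and leaves the general anaesthesia outcome untouched. It is a worthwhile improvement, not an essential correction.

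**What to change.** - Insert the name of the recruiting CFDP or CDS site into items 4 to 6. Alternatively, add one item asking which service is being rated.
- Take the between-arm satisfaction result from the wave closest to the end of treatment at that site, using the same rule in both groups.
- Report the later waves as experience of the whole pathway.
- Flag replies collected under the unnamed wording, so that the two wordings can be shown separately.

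The cost is a minor amendment and a change to the message template. Consented families are recruited through a CFDP or CDS, so the site should already be known and no new data are needed. The timetable in the Protocol (V1.4, dated 02/04/2024) runs survey rounds until August 2025, so under that timetable the later rounds could carry the new wording. The drawback is mixed wording across waves if some have already been sent.
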